## 7.2.2 Visits 2 and 3: GSP1 and GSP2

Visit 2 should occur no more than 31 days after the initial screening visit (Visit 1); both Visits 2 and 3 should occur within 14 days of Rescreening/Baseline Visit 4. Any washouts required for prohibited medications (see Section 4.3) must be completed prior to Visit 2 (GSP1).

The following activities will be conducted:

- Subject to complete the GSP assessment; will be conducted from 7:00 am to 11:00 am.
- Review the subject's health (AEs).
- Review concomitant medications/treatments.
- Schedule the subject to return for the next study visit.

#### 7.2.3 Visit 4: GSP3 (Day 1; Rescreening/Baseline) +14 Days of Visit 2

No more than 14 days may elapse between Visit 2 (GSP1) and Visit 4 (GSP3; Day 1).

The following activities will be conducted:

- Collect and review subject medical history and demographics.
- Perform physical examination including collection of height and weight (see Section 8.1.1).
- Collect vital signs (blood pressure, heart rate, respiratory rate, and temperature) after subject has been seated for >2 minutes.
- Assess inclusion/exclusion criteria.
- Subject to complete the GSP assessment; will be conducted from 7:00 am to 11:00 am.
- Subject to complete the HDSM-Ax assessment.
  - o Subject to complete PGI-S administered as Question #6 at the end of the HDSM-Ax questionnaire.
- Subjects  $\geq$  17 years of age to complete the DLQI questionnaire.
  - o 10 questions to be completed by the subject.
  - o Refer to Appendix 4.
- Perform local tolerability assessments (see Section 8.1.5).
- Review changes to the subject's health (AEs).
- Perform urine pregnancy testing (UPT) if applicable (FOCBP only). If positive, the subject shall be excluded from the study.
- Provided the subject has passed all inclusion/exclusion criteria, randomize the subject according to separate instructions.
- Pull from inventory the pump container whose unique identifier matches that assigned by the IRT system at randomization. Record the unique IP gel pump container number on the source document. Dispense study product container 1 (of 2) to the subject as follows:
  - Write subject number and initials on the study product container label.
  - o Prime the pump (5 actuations) and discard expressed gel.
  - Weigh the primed pump with the applicator cap on and record in source prior to dispensing to the subject. Dispense the pump to the subject in the kit carton with the included 2 applicators.

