#### 10.3.7 Analysis of Exploratory Efficacy Endpoints

PGI-S and PGI-C endpoints will be analyzed using a Cochran-Mantel-Haenszel test. All other exploratory efficacy endpoints that involve a proportion of responders will be analyzed using methods similar to what was described for the HDSM-Ax-7 co-primary endpoint. All other exploratory endpoints that involve a change from baseline to a single timepoint will be analyzed using methods similar to what is described for the GSP co-primary endpoint. P-values for exploratory efficacy endpoints will be provided for descriptive purposes only and no formal hypothesis testing will occur. All exploratory efficacy analyses will be based on available data and missing GSP and HDSM-Ax EOT data imputed.

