## 11.1.3 Method for Assignment to Study Product Groups

All subjects who have signed an ICF will receive a 8-digit subject screening number composed of a 1-digit study number (1), a 3-digit site number, followed by a 4-digit sequentially assigned number starting at 0001, at each site. For instance, the first subject from site 001 will have 10010001 as their assigned subject screening number; the subsequent subject from this site will have 10010002 as their assigned subject screening number. The first subject from site 002 will have 10020001 as their assigned subject screening number; the subsequent subject from this site will have 10020002 as their assigned subject screening number. This number will be unique to each subject and will be used to identify the subject throughout the study.

The randomization for this study will be stratified by investigator site. Therefore, each site will be treated as a block and a randomization schedule will be prepared in order to balance the 1:1 treatment assignment within the site. Randomization details, including block size, will be prespecified in a randomization plan.

After subjects qualify for the study (as determined by the Investigator at the Screening/Rescreening Visits), they will be randomized to sofpironium bromide, 15% or vehicle gel, and notified that their screening number becomes their post-randomization subject number. Each kit carton will contain a treatment plastic pump, which will be labeled with a unique bottle number displayed on the label. A kit will be selected from inventory and dispensed to the subject after the proper prep/priming operation (see Section 5.2).

The next eligible subject will be assigned the next available randomization slot from the randomization list queue. In this manner, eligible subjects will be randomized to the investigational product in accordance with the site-specific randomization schedule. After obtaining the kit numbers assigned from the EDC system, the Investigator will document the kit numbers dispensed to the subject by tearing off the perforated portion of the carton label and placing it on the study subject source document.

Approximately 350 subjects will be randomized to receive either sofpironium bromide gel, 15%, or vehicle gel (placebo) in a ratio of 1:1.

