### 8.1.4 Exploratory Efficacy Endpoints

Exploratory efficacy endpoints to be analyzed include the following:

- The proportion of subjects achieving at least a 1-point improvement in the HDSM-Ax-7 scale score from baseline to Days 8, 15, 22, 29, 36, 41, 42, 43 (EOT), and 57.
- The proportion of subjects achieving at least a 1-point improvement in the HDSM-Ax 11-Item (HDSM-Ax-11) scale score from baseline to Days 8, 15, 22, 29, 36, 41, 42, 43 (EOT), and 57.
- The proportion of subjects achieving at least a 2-point improvement in the HDSM-Ax-7 scale score from baseline to Days 8, 15, 22, 29, 36, 41, 42, 43 (EOT), and 57.
- The proportion of subjects achieving at least a 2-point improvement in the HDSM-Ax-11 scale score from baseline to Days 8, 15, 22, 29, 36, 41, 42, 43 (EOT), and 57.

Version: 2.0 Page 23 of 74

- The proportion of subjects achieving at least a 1-point improvement in the HDSM-Ax Question 4 score from baseline to Days 8, 15, 22, 29, 36, 41, 42, 43 (EOT), and 57.
- The proportion of subjects achieving at least a 2-point improvement in the HDSM-Ax Question 4 score from baseline to Days 8, 15, 22, 29, 36, 41, 42, 43 (EOT), and 57.
- The proportion of subjects achieving at least a 1-point improvement in the HDSM-Ax Question 5 score from baseline to Days 8, 15, 22, 29, 36, 41, 42, 43 (EOT), and 57.
- The proportion of subjects achieving at least a 2-point improvement in the HDSM-Ax Question 5 score from baseline to Days 8, 15, 22, 29, 36, 41, 42, 43 (EOT), and 57.
- Change in PGI-S from baseline to Days 8, 15, 22, 29, 36, 41, 42, 43, and 57.
- PGI-C score on Day 43.
- The proportion of subjects achieving at least a 2-point improvement in the HDSM-Ax-11 scale score from baseline to EOT and achieving at least a 70% reduction in GSP from baseline to EOT.
- The proportion of subjects achieving at least a 1-point improvement in the HDSM-Ax-11 scale score from baseline to EOT and achieving at least a 50% reduction in GSP from baseline to EOT.
- The proportion of subjects achieving at least a 2-point improvement in the HDSM-Ax-7 scale score and achieving at least a 70% reduction in GSP from baseline to Days 8, 15, 22, 29, 36, 41, 42, 43, EOT, and Day 57.
- The proportion of subjects achieving at least a 2-point improvement in the HDSM-Ax-11 scale score and achieving at least a 70% reduction in GSP from baseline to Days 8, 15, 22, 29, 36, 41, 42, 43, EOT, and Day 57.

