## 8.3.7 Exploratory Efficacy Analyses

The exploratory efficacy endpoints are fully described in Section 8.1.4. All exploratory efficacy endpoints that involve a proportion of responders will be analyzed using methods similar to what was described for the HDSM-Ax-7 co-primary endpoint. For each endpoint, a logistic regression model will be generated using planned covariates of treatment, baseline parameter, and analysis center. For the composite endpoints, both baseline HDSM-Ax and GSP will be included as covariates.

All other exploratory endpoints that involve a change from baseline to a single timepoint for a continuous variable will be analyzed using methods similar to what is described for the GSP co-primary endpoint. For each endpoint, an ANCOVA model will be generated with fixed effects for treatment, baseline parameter, and analysis center.

Version: 2.0 Page 36 of 74

Change in PGI-S from baseline and PGI-C score (only collected at Day 43) will be analyzed using a Cochran-Mantel Haenszel (CMH) test for ordinal data to compare the treatment arms at each visit.

All exploratory efficacy analyses will be based on available data and missing GSP and HDSM-Ax EOT data imputed per Section 8.2.1. HDSM-Ax-11 will be calculated in the same manner as HDSM-Ax-7 at EOT, where the mean is derived from imputed sub-items for the EOT score. In addition, all continuous parameters will be summarized by visit on the ITT population.

Data in the analysis of rank-based GSP change from baseline to each timepoint will be ranked in the same manner as that of the co-primary GSP endpoints (Section 8.3.2).

Proportion of subjects achieving 1- and 2-point improvement from baseline in HDSM-Ax-7 and HDSM-Ax-11 will be plotted at each timepoint. Similar plots will be generated for proportion of subjects achieving 50% and 70% reduction in GSP from baseline at each timepoint and for the secondary composite endpoints. Plots will be generated for change from baseline for continuous measures over time.

In addition, a summary table of frequency of missing measurements at each visit will be generated for GSP and HDSM-Ax-7, separately.

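### The CMH test for PGI-S change and PGI-C names no strata, scores or baseline term, so these descriptive comparisons may lose some available precision

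*SAP*

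**What the plan says.** For the two patient global measures, SAP 8.3.7 says that the PGI-S change and the PGI-C score will be "analyzed using a Cochran-Mantel Haenszel (CMH) test for ordinal data to compare the treatment arms at each visit". Protocol 10.3.7 says only that "PGI-S and PGI-C endpoints will be analyzed using a Cochran-Mantel-Haenszel test". Neither text states a stratification factor, the scores given to the response levels, or a baseline term. SAP 8.1.4 defines the PGI-S endpoint as "Change in PGI-S from baseline to Days 8, 15, 22, 29, 36, 41, 42, 43, and 57", so the baseline value enters by subtraction only.

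Other parts of the plan bear on this:

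- Protocol 11.1.3: "The randomization for this study will be stratified by investigator site".
- Protocol 7.2.3 (Visit 4, Day 1): "Subject to complete PGI-S administered as Question #6 at the end of the HDSM-Ax questionnaire". A baseline PGI-S is therefore collected.
- SAP 8.3.7, exploratory responder endpoints: "a logistic regression model will be generated using planned covariates of treatment, baseline parameter, and analysis center".
- SAP 8.3.7, exploratory continuous changes: "For each endpoint, an ANCOVA model will be generated with fixed effects for treatment, baseline parameter, and analysis center".
- SAP 8.2.2 defines analysis centers of at least 10 subjects for every analysis that controls for site. It does not say whether the CMH test is one of them.
- SAP 8.3.7 also says that exploratory p-values are descriptive and that no formal hypothesis testing will take place.

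**The concern.** A CMH test is built to combine evidence over strata, and here no strata are named. The analyst could run it unstratified or by analysis center, and could score the levels as integers or ranks, with nothing written in advance to settle the choice. The obvious stratum is available, because site is the randomisation factor and the center variable already exists. So is a baseline value for PGI-S. The plan uses both kinds of information for the other exploratory endpoints in the same section, and for the co-primary, supportive and secondary models in SAP 8.3.1 to 8.3.6.

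What is at stake is precision and a fixed specification for two exploratory comparisons. The trial's success criterion and its error rate are not involved.

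**Working it through.** The plan states no power or precision for PGI-S or PGI-C, so there is no figure to reproduce. It also gives no correlation, spread or site effect for either measure. The values of r, k, rho and ICC below are assumptions.

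**1. Baseline adjustment of PGI-S.** Let s be the follow-up SD, k the ratio of baseline SD to follow-up SD, and r the correlation between baseline and follow-up.

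- Variance of the change score: s²(1 + k² − 2rk)
- Variance after linear adjustment for baseline: s²(1 − r²)
- Ratio: (1 − r²) / (1 + k² − 2rk), which becomes (1 + r)/2 when k = 1

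Example at r = 0.2. With k = 1 the ratio is 1.2/2 = 0.60, a 40% reduction. With k = 0.7 it is 0.96/1.21 = 0.79, a 21% reduction. With k = 0.5 it is 0.96/1.05 = 0.91, a 9% reduction.

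| r | Reduction, k = 1 | Reduction, k = 0.7 | Reduction, k = 0.5 |
|---|---|---|---|
| 0.2 | 40% | 21% | 9% |
| 0.3 | 35% | 15% | 4% |
| 0.5 | 25% | 5% | 0% |
| 0.6 | 20% | 1.5% | 1.5% |

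A value of k below 1 is plausible. Protocol 4.2 admits only subjects with HDSM-Ax-7 of 3 to 4, on a 0 to 4 scale, at Visits 1 and 4. PGI-S is not itself an entry criterion, but it is a 0 to 4 severity item on the same questionnaire.

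**2. Center strata.** Stratifying by center removes a share of variance of about the site intraclass correlation (ICC): 0 to 10% for an assumed ICC of 0 to 0.10. With at least 10 subjects per center there are at most 300/10 = 30 strata among the evaluable subjects, or 350/10 = 35 among those randomised.

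**3. Simulation.** This used 300 subjects in 30 centers of 10, 1:1 within center, and a 0 to 4 follow-up score. Baseline was limited to the top three levels (2 to 4), so its range was narrower than at follow-up. The assumed latent effect was 0.33 SD, the test was two-sided at 0.05, and there were 2000 runs per setting. The CMH statistic was the row-mean-score test on integer scores. Here rho is the latent correlation. The last two columns use a single post-baseline 5-level score as a stand-in for PGI-C, which has 7 levels.

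| rho, ICC | PGI-S change, no strata | PGI-S change, center strata | PGI-S change, ANCOVA with baseline and center | PGI-C-like, no strata | PGI-C-like, center strata |
|---|---|---|---|---|---|
| 0.1, 0 | 0.696 | 0.694 | 0.768 | 0.767 | 0.766 |
| 0.1, 0.10 | 0.708 | 0.727 | 0.830 | 0.789 | 0.818 |
| 0.3, 0.05 | 0.756 | 0.766 | 0.818 | 0.774 | 0.786 |
| 0.3, 0.10 | 0.780 | 0.804 | 0.854 | 0.796 | 0.817 |
| 0.5, 0 | 0.844 | 0.842 | 0.854 | 0.776 | 0.778 |
| 0.5, 0.10 | 0.856 | 0.876 | 0.886 | 0.789 | 0.802 |

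Over all nine settings run (rho 0.1, 0.3, 0.5; ICC 0, 0.05, 0.10):

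- Center strata alone added about 0 to 2 points for PGI-S change (largest gain 0.804 − 0.780 = 0.024) and about 0 to 3 for the PGI-C-like score (largest 0.818 − 0.789 = 0.029).
- Baseline and center together added about 1 to 12 points for PGI-S change (0.854 − 0.844 = 0.010 up to 0.830 − 0.708 = 0.122).
- With no treatment effect, the unstratified tests rejected in 0.034 to 0.060 of runs. The simulation error is about √(0.05 × 0.95/2000) = 0.005, so there is no sign of inflation, and the lower rates occur mostly as the ICC rises.

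**The case against.** The strongest reply is that silence is not exclusion. A CMH test can be stratified, SAP 8.2.2 supplies the center variable, and the table specifications sit in a separate document. That stands. A reader might infer that the plan rejects adjustment for site, but the text only leaves the strata open.

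Four further points limit the concern, and all of them stand:

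- PGI-C asks about change since starting treatment and is collected once, at Day 43. It has no baseline value of its own, so the missing baseline term concerns PGI-S only. There, subtraction already uses the baseline, and the loss is relative to covariate adjustment.
- The 20 to 40% variance reduction needs equal baseline and follow-up variances. A reader might take it as the loss in this trial. The documents give neither the correlation nor the spreads, and the entry criteria point towards a narrower baseline.
- PGI-S and PGI-C are also anchors for the psychometric evaluation of HDSM-Ax-7, so a reader might infer that this work suffers. It rests on correlations and runs under a separate plan (Protocol 10.3.8, SAP 11.1). Nothing says that the between-arm CMH result feeds it.
- The method was chosen deliberately. Amendment 03 added the CMH test, and SAP 8.3.7 keeps ANCOVA for continuous variables. A separate method for ordinal items is a fair choice.

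The last point explains why a CMH test was chosen. It does not explain why that test has no named stratum or scores when site is the randomisation factor.

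**Conclusion.** The concern holds as a minor one. The CMH specification for PGI-S change and PGI-C is incomplete, and run unstratified and unadjusted it would lose some precision that the collected data could supply.

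The site part is small, about 0 to 3 power points under an assumed ICC of 0 to 0.10. The baseline part applies to PGI-S only and could be larger or close to nothing: a 20 to 40% lower variance for r of 0.6 to 0.2 at equal spreads, and about 0 to 20% at an SD ratio of 0.5 to 0.7. These sizes rest on assumed values.

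A reader might go further and conclude that the test is invalid or inflates false positives. Neither the documents nor the simulation supports that. The comparisons lie outside the gated testing sequence of SAP 8.2.4, and their p-values are descriptive.

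**What to change.** In SAP 8.3.7:

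- For PGI-C and PGI-S change, specify the CMH row-mean-score test, state the scores, and stratify by analysis center as defined in SAP 8.2.2. Say that the collapsing steps already given there (35, then 70 subjects per center, then dropping the term) also apply here if centers prove too sparse.
- For PGI-S, also adjust for baseline PGI-S, for example by a rank ANCOVA of PGI-S change with treatment, baseline PGI-S and analysis center. State which of the two PGI-S results is the main one.

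This keeps the listed change endpoint. A proportional-odds model of the visit score is not needed: it would replace that endpoint, and with up to about 30 center terms it could run into the small-cell problems that SAP 8.2.2 anticipates.

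The cost is a few sentences, minor programming, and an entry in SAP Section 13 because the protocol names only a CMH test. No extra data are required.

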#### 8.4 Examination of Subgroups

While the study is not powered to show efficacy for pre-defined subgroups, the coprimary efficacy end points will be further analyzed by subgroups of interest. All p-values from the subgroup tables will be of an exploratory nature, as no formal hypothesis testing will occur.

The primary analyses for the primary endpoints (see sections 8.3.1 and 8.3.2) will be repeated for the ITT population for the following subgroups:

- Age group: < 17 years,  $\ge 17$  to 30 years,  $\ge 31$  years.
- Gender: male, female.
- Ethnicity: Hispanic or Latino, Not Hispanic or Latino or not reported.
- Race: white, non-white or not reported.

Version: 2.0 Page 37 of 74

Brickell Biotech, Inc. Protocol No. BBI-4000-CL-301

Race and ethnicity categories have been combined due to potential small sample size. For age group, should the models fail to converge due to small cell size, age categories may be further collapsed. For all subgroup models, should the models fail to converge, NA or not assessable or similar will be displayed.

Version: 2.0 Page 38 of 74

#### 9. SAFETY EVALUATION

## 9.1 Overview of Safety Analysis Methods

Safety analyses will be carried out for the Safety Population. Subjects who do not complete the study, for whatever reason, will have all available data up until the time of termination included in the analyses. Allowable windows for each study visit are laid out in the Schedule of Events in Section 18.1. Assessments that occur outside of the allowable window for each study visit will be flagged as protocol deviations, but will be used in all safety analyses. In general, all data will be associated with the nominal study visit for which it was collected. Repeat assessments and unscheduled visits will be included in study listings, but will not be used in place of nominal timepoint data. It is not expected that there will be multiple measurements that occur within the same assessment time window. Should that occur, the closest measurement will be used in the analysis; an earlier measure will be used in case of a tie. No formal hypothesis testing will be performed.

#### 9.2 Adverse Events

Treatment-emergent adverse events (TEAEs) are defined as those adverse events (AEs) with onset during or after the first dose of study drug or existing events that worsened after the first dose during the study. Treatment-emergent AEs will be summarized by treatment group and severity.

Partial or completely missing AE start dates will be imputed as follows:

- 1. If the year and month are known:
  - a. If the year and month are the same as the year and month of the treatment start date, impute to treatment start date.
  - b. Otherwise, use the 1st of the month.
- 2. If only the year is known:
  - a. If the year is the same as the year of treatment start date, impute to treatment start date.
  - b. Otherwise, impute to January 1st of that year.
- 3. If the date is completely missing, impute to treatment start date.

Partial or completely missing AE end dates will be imputed in the same manner, with end of treatment date or end of study date.

AE listings will display the imputed dates.

Verbatim terms on case report forms will be mapped to preferred terms and system organ classes using the latest version of MedDRA.

Version: 2.0 Page 39 of 74

At Visits 5, 6, 7, 8, 9, 12 (EOT), and 13 (Follow-up), treatment-emergent adverse events (TEAEs) in the Safety Population will be summarized by severity in the following tables: all reported TEAEs, all SAEs, all treatment-related SAEs, treatment-related TEAEs, severe TEAEs, TEAEs leading to dose interruption, TEAEs leading to study discontinuation, TEAEs of special interest, and anticholinergic TEAEs. Additionally, local site reaction TEAEs will be summarized in the Safety Population by severity at Visits 5, 6, 7, 8, 9, 12 (EOT), and Visit 13 (Follow-up). Local site reaction TEAEs are defined as AEs coded to the system organ class of general disorders and administration site conditions and, at a minimum, the following preferred terms:

- Application site pruritus
- Application site pain
- Application site irritation
- Application site dermatitis
- Application site rash
- Application site erythema
- Application site discolouration
- Application site dryness
- Application site exfoliation
- Application site reaction
- Application site warmth

Each of the above tables will be produced for cumulative TEAEs up to the current visit reported by all Safety Population subjects (including those absent from the current visit). At each of the visits, each of the above tables will summarize the subject incidence (frequency count and %) for the specified TEAE, mapped to MedDRA System Organ Class and Preferred Term, according to the highest severity reported. Subjects with only unknown severity for a TEAE will be counted under the severity unknown category.

Summaries that are displayed by system organ class and preferred terms will be ordered by descending incidence of system organ class in the total column and preferred term within each system organ class. The total column will not be displayed and will only be used for sorting. TEAEs of special interest include the following:

- Vision blurred
- Mydriasis (unilateral or bilateral)
- Urinary hesitation

An overall TEAE summary table by treatment group with the total number of TEAEs and the number and percentage of subjects with at least one of the following will be presented: TEAE, serious TEAE, treatment-related TEAE, treatment-related serious TEAE, severe TEAE, TEAE leading to dose interruption, TEAE leading to study discontinuation, TEAEs of special interest, anticholinergic TEAEs, anticholinergic TEAEs leading to study discontinuation, local site reaction TEAEs, local site reaction TEAEs leading to study discontinuation. The overall summary table will also display the number and percent of subject deaths, should any deaths occur.

Version: 2.0 Page 40 of 74

The number of subjects with study discontinuations due to TEAEs, the number of subjects with study discontinuations due to anticholinergic TEAEs, and the number of subjects with study discontinuations due to AESIs will be plotted as a bar chart versus time on treatment. Time on treatment is defined as the earlier of treatment end date or study discontinuation date – treatment start date + 1. Time on treatment will be displayed in categories of 0 to 2 weeks, >2 to 4 weeks, >4 to 6 weeks. Weeks are defined as 7 days. The follow-up visit is excluded.

The number of treatment-related TEAEs and the number of local site reaction TEAEs will be plotted versus time on treatment. The number of subjects with a treatment-related TEAE and the number of subjects with a local site reaction TEAE will be plotted versus time. Time for these plots will be displayed as weeks 1-8 which includes the follow-up visit.

Adverse event data will be presented in data listings by subject, treatment group, and event. SAEs, TEAEs leading to study discontinuation, TEAEs of special interest, and anticholinergic TEAEs will be presented in separate data listings. Death is not expected. However, should death occur on study, the event will be reported with detailed narratives.

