#### 9.2 Adverse Events

#### 9.2.1 Definitions of Adverse Events

According to 21 CFR Parts 312.32 and 320.32 (IND Safety Reporting, Applicability of Requirements Regarding an "Investigational New Drug Application"), Food and Drug Administration (FDA) Guidance for Industry (Investigational New Drug Safety Reporting Requirements for Human Drug and Biological Products and Safety Reporting Requirements for Bioavailability and Bioequivalence Studies in Humans) (Federal Register/Vol. 75, No. 188/September 29, 2010) and International Council on Harmonisation (ICH) E2A (Clinical Safety and Data Management: Definitions and Standards for Expedited Reporting):

An adverse event (AE) means any untoward medical occurrence associated with the use of a drug in humans, whether or not considered drug related.

A suspected adverse reaction (SAR) means any AE for which there is a reasonable possibility that the drug caused the AE.

The following information should be considered when determining whether or not to classify a test result, medical condition, or other incident as an AE:

Adverse events will be recorded from the time of informed consent.

Abnormal laboratory values should not generally be recorded as AEs unless an intervention is required, the laboratory abnormality results in an SAE, the lab abnormality results in study termination or interruption/discontinuation of study treatment, or the lab abnormality is associated with clinical signs or symptoms. When recording an AE resulting from a laboratory abnormality, the resulting medical condition rather than the abnormality itself should be recorded (e.g., record "anemia" rather than "low hemoglobin").

Complications that occur in association with a protocol-mandated intervention (e.g., invasive procedures such as biopsies) should be recorded as AEs.

Whenever possible, the Investigator should group signs or symptoms that constitute a single diagnosis under a single event term. For example, cough, rhinitis, and sneezing might be grouped together as "upper respiratory tract infection." If possible, abnormal laboratory results that meet the definition of an AE (see above) should be reported as a clinical diagnosis rather than the abnormal value itself (e.g., "anemia" rather than "decreased blood count").

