#### 9.5.3 Other Safety Measures

#### 9.5.3.1 Prior and Concomitant Medications

Medications will be coded using the latest version of the World Health Organization (WHO) drug dictionary. Medications entered on the eCRF will be mapped to Anatomic Therapeutic Chemical (ATC) drug class (level 4) and drug name.

Prior and concomitant medications will be summarized separately and the study phase of each medication will be determined programmatically based on medication start and end dates. Partial or missing start and end dates will be imputed according to Section 9.2.

A prior medication is defined as any medication started prior to the date of the first dose of study drug. A concomitant medication is defined as any medication started on or after the date of the first dose of study drug.

For the summary of both prior medications and concomitant medications, the number and percentage of subjects receiving any medication will be summarized by treatment group,

Version: 2.0 Page 42 of 74

as will the number and percentage receiving any medication by ATC drug class and generic drug name. Subjects reporting use of more than one medication at each level of summarization (any medication received, ATC class, and generic drug name) will be counted only once. ATC class terms will be displayed by descending order of incidence, as will generic drug names within each ATC class. The study phase during which each medication was received (e.g., prior, concomitant,) will be presented on the listing of prior and concomitant medications.

Prior or concomitant therapies and procedures will be listed only.

Version: 2.0 Page 43 of 74

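### SAP 9.2 imputes each adverse event date without checking the event's other recorded date, so a resolved screening event can be counted as treatment-emergent and an imputed end can precede onset

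*SAP*

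**What the plan says.** SAP 9.2 defines treatment-emergent adverse events (TEAEs) by onset, as "those adverse events (AEs) with onset during or after the first dose of study drug", plus existing events that worsen after the first dose. It then gives a three-step rule for incomplete onset dates.

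- **Year and month known:** "If the year and month are the same as the year and month of the treatment start date, impute to treatment start date". Otherwise the 1st of the known month is used.
- **Only the year known:** "If the year is the same as the year of treatment start date, impute to treatment start date". Otherwise 1 January of the known year is used.
- **Nothing known:** "If the date is completely missing, impute to treatment start date".

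For end dates there is one sentence: "Partial or completely missing AE end dates will be imputed in the same manner, with end of treatment date or end of study date". The results are shown to the reader: "AE listings will display the imputed dates".

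The rule is reused for medications in SAP 9.5.3.1: "Partial or missing start and end dates will be imputed according to Section 9.2". That section defines a prior medication as one started before the date of first dose, and a concomitant medication as one started on or after it.

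Pre-dose events are expected. Protocol 9.2.1 says "Adverse events will be recorded from the time of informed consent". Protocol 7.2.1 allows screening up to 45 days before Visit 4, and the SAP plans a listing of screening period AEs (16.2.7.4). Protocol 9.2.1.2 has both the start and the resolution date recorded for every AE, so one can be known when the other is not.

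**The concern.** The rule works on one date at a time. Nothing in SAP 9.2 compares an imputed onset with a recorded end, or an imputed end with a recorded onset, and no other section adds such a check.

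For onsets, an event that the record itself shows to be over before first dose can be moved to Day 1. It then meets the onset-based TEAE definition and enters the cumulative TEAE tables for Visits 5 to 9, 12 and 13. For end dates, the listings can show an event ending before it began. For medications, a drug stopped in screening can be reported as started on treatment. That is a realistic setting, because Protocol 6 records drugs needing washout and Protocol 7.2.2 requires washout to be complete before Visit 2.

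At stake are the accuracy of the TEAE counts, the credibility of the listings and the prior/concomitant split. Two programmers could also follow the end-date sentence and produce different dates.

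**Working it through.** The plan states no figure for this point, so there is none to reproduce. The check applies the written rules to example dates and then enumerates them.

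**1. Onset, worked example.** First dose is 20 March 2021. The AE has onset March 2021 (day unknown) and known end 8 March 2021. The onset month equals the first-dose month, so imputed onset is 20 March. Onset minus end = 20 − 8 = 12 days, so onset follows the end, and the event meets the TEAE definition. With only the year known, or nothing known, the result is again 20 March.

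**2. Onset, enumeration.** Assume one-day events with a known end on each of the 45 days before first dose, and each of the 365 days of 2021 as first dose: 365 × 45 = 16,425 combinations, weighted equally. An event is wrongly made a TEAE in these cases.

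- *Month and year known:* when the event falls in the first-dose month. A first dose on day d of a month has d − 1 such days. Summed over the year this is 7 × 465 + 4 × 435 + 378 = 5,373, and 5,373 / 16,425 = 32.7%. The other combinations stay pre-treatment.
- *Year only:* the first 45 start days of the year contribute 0 + 1 + … + 44 = 990, and the remaining 320 contribute 45 each, or 14,400. 15,390 / 16,425 = 93.7%.
- *Nothing known:* 100%.

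**3. End date, month known.** Onset is 12 May, end is recorded as May, and treatment and study both end in June. May is not the reference month under either choice, so the imputed end is 1 May, 12 − 1 = 11 days before onset. For onsets enumerated over study days 1 to 57 (365 × 57 = 20,805 combinations), with the end month known and equal to the onset month, the imputed end precedes onset in 14,748, or 70.9%. The share is the same whether the reference is Day 42, Day 43 or Day 57.

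**4. End date, fully missing.** First dose on 20 March puts Day 43 on 1 May and Day 57 on 15 May. For an AE with onset 10 May:

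| Reference date | Imputed end | Before onset? |
|---|---|---|
| End of treatment (Day 43) | 1 May | Yes |
| End of study (Day 57) | 15 May | No |

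Over study days 1 to 57, the end precedes onset for 14 / 57 = 24.6% of onset days with Day 43 as reference, 15 / 57 = 26.3% with Day 42 (last dose), and 0% with Day 57. The SAP does not say which applies.

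**5. Medications.** A fully missing start, or a partial start matching the first-dose month or year, becomes the first-dose date. That meets the definition of concomitant even when the recorded stop date is earlier.

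**6. After a two-way bound.** Capping the imputed start at a known end, and holding the imputed end at or after a known start, gave 0 inversions and 0 false TEAEs in the same enumeration, for all three kinds of incomplete date and all three reference days.

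The percentages are shares of equally weighted calendar combinations. They are not expected AE rates.

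**The case against.** Treating an unknown onset as treatment-emergent is an accepted conservative convention in safety reporting. That stands. The problem is confined to records where a known end date rules the convention out.

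Such records should be few. AEs are reviewed at Visits 2, 3 and 4, both dates are collected, and data clarification precedes database lock. This also stands, and it limits the size of the effect without making the rule correct. The end-date sentence is brief and does not restate the first-of-month step, so the table, figure and listing specifications, held in a separate document not available here, might resolve it. The literal reading is nevertheless the one described.

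A reader might go further in three ways that the documents do not support.

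- **Every incomplete onset goes to first dose.** It does not. A partial onset in a different month goes to the 1st of that month, and a year-only onset in an earlier year goes to 1 January. Both stay pre-treatment.
- **AE durations turn negative.** The dates in step 3 would give 1 − 12 + 1 = −10 days if an end − start + 1 formula were used, but the SAP defines and tabulates no AE duration. It uses that formula for exposure, time on treatment and time since symptom onset. SAP 3.2 says only that dates in duration calculations may be imputed by similar logic. AE end dates do not enter the TEAE definition either, so the visible effect of the end-date rule is in the listings.
- **Every medication with an unknown start is mislabelled.** A long-term drug with a known earlier year goes to 1 January of that year and is correctly prior. Where to place a drug with both dates unknown is a matter of convention. The clear error is the one with a recorded stop before first dose.

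**Conclusion.** The point holds. SAP 9.2 states a rule that gives a wrong result whenever an AE has a recorded end before first dose and an onset that is fully missing, or partial and matching the first-dose month (or year, if only the year is known). The same gap lets a month-only end date fall before a known onset. If end of treatment is the reference, a follow-up AE with a missing end date would end before it began. Through 9.5.3.1, some medications stopped before first dose are labelled as started on Day 1.

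The effect is limited to TEAE counts, AE listings and medication phase. It does not reach the co-primary or other efficacy analyses. It is probably small, but it cannot be sized, because the documents do not give the number of incomplete dates. The conclusion assumes that imputed onset determines TEAE status, which the SAP implies by placing the imputation rules directly after the onset-based definition. This is an improvement worth making, and it does not threaten the trial's main conclusions.

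**What to change.** In SAP 9.2:

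- Impute onset to treatment start only if the end date is missing or is on or after first dose.
- Otherwise set onset no later than the known end date, within the known parts of the onset. If onset is fully missing, use the consent date or the end date, whichever is earlier. Do not count the event as a TEAE unless it worsened after first dose.
- Impute a partial end date to the last day of the known month or year, capped at end of study and never before onset. Name end of study as the single reference date.

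In SAP 9.5.3.1, classify a medication whose known stop date precedes first dose as prior, whatever its imputed start.

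This keeps the conservative default where onset is truly unknown. It costs a few sentences in two SAP sections and a small programming change, and needs no new data.
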